9.2 Screening visit (Visit 1)

After written informed consent has been obtained, a unique Screening Number (Subject ID) will be assigned and screening assessments may commence.

During the screening procedure, Days -28 to Day – 1 inclusive, subjects will undergo screening assessments including medical history, height, weight, 12-lead ECG, vital signs, and full physical examination. In addition to eligibility criteria, medical history will include details of history of migraine headaches, average duration (shortest and longest), description of nature (throbbing, aggravating factors, unilateral/bilateral, aura), severity and associated symptoms including most troublesome symptom and relationship to menstrual cycle (menstruating females).

Concomitant medications will be recorded. Blood will be collected for routine haematology and biochemistry screening and, in female subjects of child-bearing potential, to test for pregnancy. A urine sample will be collected for urinalysis.

Subjects deemed likely to be eligible for the trial will be given two diaries after completion of the above screening tests, shown how to record and to list concomitant medications. The headache diary will be used to record menstrual cycles, and onset and nature of headaches (both migraine and non-migraine). In addition, they will be instructed to complete a migraine diary during a migraine headache to collect pain and symptom scores and concomitant medications. Scores will be recorded before taking their usual migraine medication and at 0.5, 1.0, 1.5, 2, 4, 8 and 24 hours after taking their usual migraine medication. The screening diaries will be completed for a minimum of 28 days. If the subject does not experience a migraine headache in this period or menstrual bleeding (menstruating females only), the screening diary period may be extended by 7 days, ie up to 35 days total.

Note that diary entries completed prior to Day 1 will be used only to confirm compliance with diary completion requirements on the day of a migraine headache, to verify the nature of migraine headache and the subject's most troublesome symptom.

9.3 First treatment period (Visit 2)

Subjects will return to the unit on Day 1 (Visit 2) with their diaries completed from Day -28 to Day -1 inclusive. If a subject has not experienced a migraine headache or menstrual bleeding (menstruating females only) during the 28-day period, the screening diary period may be extended to 35 days.

On Day 1, assessments including 12-lead ECG, vital signs, a targeted physical examination, recording of concomitant medications, review of the subject's diaries, blood and urine sampling for safety monitoring, and urine sampling for pregnancy testing in FOCBP, will be conducted. Results from safety monitoring tests are not required prior to randomisation.

Eligibility will be confirmed and subjects will be randomised to LAT8881 60 mg or placebo.

Subjects will leave the unit with their two diaries, and one dose of IMP and instructions to take the dose within one hour of the onset of a migraine headache of moderate to severe intensity (NRS ≥ 4). The headache diary will be used to record menstrual cycles and onset and nature of headaches (both migraine and non-migraine). The migraine diary will be used during a migraine headache to collect pain and symptom scores and concomitant medications before taking the IMP and at 0.5, 1.0, 1.5, 2, 4, 8 and 24 hours after taking the dose. No analgesics or antimigraine medication other than medications for routine prophylaxis not on the Prohibited medicines list may be taken within 24 hours prior to taking the dose of IMP. Rescue medication is permitted a minimum of 2 hours post dose. The subject's symptoms including nausea, photophobia and phonophobia plus the subject's most troublesome symptom if other than nausea, photophobia or phonophobia will be recorded immediately before dosing and at 0.5, 1.0, 1.5, 2, 4, 8 and 24 hours after taking the dose. Episodes of vomiting will also be recorded.

The subject will be instructed to phone the clinic within 24 hours (or one business day) of taking the dose.

On Day 15, if the subject has not phoned the clinic, the subject will be phoned to remind them to complete their diaries, and to phone the clinic when the dose has been taken.

Subjects will return to the clinic for Visit 3 within 5 business days after taking the dose or a maximum of 28 days after Visit 2. Subjects should be reminded to bring their diaries and medication container to the visit.

9.4 Visit 3

Assessments including 12-lead ECG vital signs, a targeted physical examination and concomitant medications will be recorded and the subject's diaries will be reviewed. Blood and urine samples will be taken for safety monitoring and pregnancy testing (FOCBP). Subject satisfaction with Treatment Period 1 IMP will be recorded (if dose taken). Results from safety monitoring tests are not required prior to dosing.

Treatment period 2

Subjects will leave the clinic with their diaries and one dose of IMP (alternate treatment), to take the dose within one hour of the onset of a migraine of moderate to severe intensity (NRS ≥ 4), but not less than 48 hours after last dose, and instructions to complete the diaries as for Treatment period 1. No analgesics or antimigraine medication other than medications for routine prophylaxis not on the Prohibited medicines list may be taken within 24 hours prior to taking the dose of IMP. Rescue medication is permitted a minimum of 2 hours post dose.

The subject's symptoms including, nausea, photophobia and phonophobia plus the subject's most troublesome symptom if other than nausea, photophobia or phonophobia will be recorded at the time of dosing and at 0.5, 1.0, 1.5, 2, 4, 8 and 24 hours after taking the dose. Episodes of vomiting will also be recorded

The subject will be instructed to phone the clinic within 24 hours (or one business day) of taking the second dose.

If the subject has not phoned the clinic, the subject will be phoned 14 days after Visit 3 to remind them to complete their diaries, and to phone the clinic when the dose has been taken.

Subjects will return to the clinic for Visit 4 within 5 business days after taking the dose or a maximum of 28 days after Visit 3.

9.5 End of second treatment period (Visit 4)

Subjects will return to the clinic with their diaries and medication containers at completion of Treatment Period 2.

Blood and urine samples will be taken for safety analysis. 12-lead ECG, vital signs, concomitant medications, targeted physical examination results and adverse events will be recorded. Subjects will be asked to complete assessments for subject satisfaction for Treatment period 2, if dose taken and overall preference for Treatment 1 or 2 if both doses have been taken.

9.6 End of study (Visit 5)

Subjects will be phoned one week after Visit 4 to review any new or changed adverse events or changes in concomitant medications.

9.7 Early withdrawal visit

An early withdrawal visit should be conducted within one week of the subject withdrawal, and/or a minimum 48 hours after last dose of IMP.

Subjects who are completing an early withdrawal visit will return with their diaries and unused IMP.

Blood and urine samples will be taken for safety analysis. 12-lead ECG, vital signs, concomitant medications, targeted physical examination results and adverse events will be recorded. Subjects will be asked to complete assessments for subject satisfaction.

10. Study endpoints

10.1 Primary endpoint

Change in migraine headache pain score, using an 11-point NRS, (0 = none, 10 = worst imaginable), from the time of dosing (t = 0 min) to 0.5, 1.0, 1.5, 2, 4, 8 and 24 hours post dose. Pain is recorded in a subject diary and should reflect the subject's pain at the time of recording.

10.2 Secondary endpoints

1. Change in migraine-associated symptoms of nausea, photophobia and phonophobia. Symptoms are assessed on an 11- point Likert scale with 0 = no symptoms and 10 being severe symptoms at time of dosing and at 0.5, 1.0, 1.5, 2, 4, 8 and 24 hours post dose.
2. Change in each subject's most troublesome symptom that may include nausea, photophobia and phonophobia cognitive impairment, dizziness and functional disability. Symptoms are assessed on an 11- point Likert scale with 0 = no symptoms and 10 being severe symptoms at time of dosing and at 0.5, 1.0, 1.5, 2, 4, 8 and 24 hours post dose.
3. The percentage of subjects achieving "no headache pain" at 0.5, 1.0, 1.5, 2, 4 and 8 hours post dose

10.3 Safety endpoints

1. Changes in physical examinations and vital signs
2. Changes in clinical laboratory tests
3. Percentage of Treatment emergent adverse events (TEAEs), including serious adverse events (SAEs), and suspected unexpected serious adverse reactions (SUSARs)
4. Changes in concomitant medications

10.4 Exploratory endpoints

1. The percentage of subjects who are "sustained pain-free," defined as having no migraine headache pain at 24 hours, with no use of rescue medication and no relapse of headache pain within 24 hours (24-hour sustained pain-free) after administration
2. The time to first pain-free timepoint following treatment with oral LAT8881 compared with placebo to 24 hours post dose, with no use of rescue medication
3. Supplemental analgesic medication use in the 24 hour post treatment period
4. Subject satisfaction with each treatment based on a 7-point Likert Scale, overall preference for Treatment 1 or Treatment 2, and historical comparison with usual treatment
5. Association between change in headache pain and symptom scores and selected subject baseline characteristics, including for example, migraine with/without aura, relationship to menstrual cycle

11. Study measurements

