3.1 Acute migraine

Migraine is a disabling neurovascular disorder, characterised by moderate to severe headaches which are usually throbbing, affect one side of the head and are accompanied by nausea and sensitivity to light and/or sound. It is one of the most common chronic conditions worldwide.

The most common migraine types are migraine without aura (common migraine) and migraine with aura (classic migraine).³

Migraine without aura is identified by headache symptoms lasting 4–72 hours, commonly with a unilateral location, pulsating quality of moderate or severe intensity, aggravated by routine physical activity and associated with nausea and/or light and sound sensitivity. Diagnosis is based on at least five attacks.³

Migraine with aura is identified by recurrent attacks, lasting minutes, of unilateral fully reversible visual, sensory or other central nervous system symptoms that usually develop gradually and are commonly followed by headache and associated migraine symptoms. Diagnosis of migraine with aura requires at least two such attacks.³

Recognition of the pathophysiology of migraine has evolved from the belief that it was a primary consequence of intracranial vasodilation, to the more recent theory that it is initiated by a complex series of neural and vascular events.⁴ According to this theory, migraine is primarily a neurogenic process with secondary changes in cerebral perfusion. The headache pain itself is considered to be due to activation of the trigeminovascular pathway, but it has been suggested that there are multiple neuronal functional abnormalities which are involved in the initiation of a migraine.⁵

Migraine prevalence is reported to be between 2.6% and 21.7%, with an average of approximately 12%.⁶ In the 2016 Global Burden of Disease Study,⁷ migraine (including medication overuse headache) ranked in the top ten of years lived with disability in all 195 countries and territories investigated, and overall was the second largest cause of disability.

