4.3 Exploratory objectives

1. To investigate the percentage of subjects who are “sustained pain-free,” defined as having no headache pain following treatment with oral LAT8881 compared with placebo, with no use of rescue medication and no relapse of headache pain within 24 hours (24-hour sustained pain-free) after administration
2. To investigate the time to first pain-free timepoint following treatment with oral LAT8881 compared with placebo to 24 hours post dose, with no use of rescue medication
3. To determine the need for extra analgesic (rescue) medication after treatment with oral LAT8881 administration, compared with placebo
4. To investigate subject satisfaction with treatment
5. To investigate other factors influencing the extent of change in pain score and symptom scores in subjects with migraine

5. Study design

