11.5 Efficacy assessments

11.5.1 Pain intensity

Migraine pain intensity will be recorded using the NRS in a subject migraine diary at the start of dosing (t

= 0 min) and at 0.5, 1.0, 1.5, 2, 4, 8 and 24 hours post dose. The NRS is an 11-point scale which grades pain from 0 (no pain) to 10 (worst pain imaginable). Pain should reflect the subject's pain at the time of recording.

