### 10.15.2 Sustained Pain-Free

Subjects having no use of rescue medication and no relapse of headache pain within 24 hours after administration of IMP in each period will be separately flagged as ‘Sustained Pain-free’ for analysis.

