### 10.15.4 Responder

Subjects achieving no migraine headache pain at each time point in each study period will be separately flagged for analysis. Presence or absence of pain will be determined as follows:

- Absence: NRS Pain score 0 or 1 at the corresponding timepoint.
- Presence: NRS Pain score more than 1 at the corresponding timepoint.

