### 11.8.3 Exploratory Analysis

#### 11.8.3.1 Sustained Pain-free at 24 Hours

Number and percentage of subjects who are “sustained pain-free” at 24 hours (as defined in section 10.15.1) will be summarised treatment overall. The paired difference in number of subjects sustained pain-free (LAT8881 – Placebo) will be calculated as mentioned in section 10.16.

The summary will be based on Per-Protocol population.

In DDP: Table 14.2.5

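### 24-hour sustained pain-free sets no time by which pain freedom must begin, so an attack that hurts through 8 h and is over at 24 h without rescue counts as sustained

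*Protocol*

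**What the plan says.** Protocol 10.4 defines the endpoint as "having no migraine headache pain at 24 hours, with no use of rescue medication and no relapse of headache pain within 24 hours"; the Protocol synopsis and SAP 7.4 repeat it. The matching objective in Protocol 4.3 is "defined as having no headache pain following treatment with oral LAT8881 compared with placebo, with no use of rescue medication and no relapse", again with no time for becoming pain-free. Protocol 14.5 adds only that counts, percentages and a two-way table will be shown.

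The SAP derivation in 10.15.2 flags "Subjects having no use of rescue medication and no relapse of headache pain within 24 hours after administration of IMP in each period". It adds no start time, and it also leaves out the requirement to be pain-free at 24 h. SAP 11.8.3.1 cites 10.15.1 for the definition, but that section covers the difference between treatments. On the analysis it says: "The paired difference in number of subjects sustained pain-free (LAT8881 – Placebo) will be calculated as mentioned in section 10.16". No test is specified.

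Pain-free is set in SAP 10.15.4: "Absence: NRS Pain score 0 or 1 at the corresponding timepoint". Protocol 11.5.1 has pain scored "at 0.5, 1.0, 1.5, 2, 4, 8 and 24 hours post dose", so nothing is recorded between 8 h and 24 h. Rescue is permitted from 2 h (Protocol 8.2.3).

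**The concern.** *Sustained* and *relapse* make sense only if pain freedom came first and was then held. The definition does not require that. A subject who was never pain-free by 8 h cannot relapse, so that condition is met by default and only two remain: no pain at 24 h and no rescue.

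Protocol 3.1 makes such records plausible: "Migraine without aura is identified by headache symptoms lasting 4–72 hours". An attack that ends between 8 h and 24 h lies inside that range. The report would then describe people who hurt for at least 8 h after dosing as sustained pain-free. The treatment comparison would mix held responses with attacks that had simply ended by the next day. A sustained pain-free percentage is easy to misread, and Protocol 5.3 plans dose-response work after this study.

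**Working it through.** **Reading the rule against one record.** Take NRS 6, 6, 6, 6, 5, 4, 0 at 0.5, 1, 1.5, 2, 4, 8 and 24 h, with no rescue.

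- No pain at 24 h (score 0): met.
- No rescue: met.
- No relapse within 24 h: met, because there was no earlier pain-free score to relapse from.
- Result under Protocol 10.4 and SAP 7.4: sustained pain-free.
- Secondary endpoint (Protocol 10.2, item 3: 0.5, 1, 1.5, 2, 4 and 8 h): fails at all six timepoints.
- First pain-free timepoint (SAP 10.15.5): 24 h, the slowest category available.

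Restoring the missing 24 h condition in SAP 10.15.2 would not change this, because the record meets that condition.

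**Effect on the comparison.** The plan states no rate for this endpoint, so there is no figure to reproduce and every rate below is an assumption. Let p be the proportion pain-free by 8 h who hold it to 24 h without rescue. Let q be the share of the remaining subjects who hurt through 8 h, take no rescue and score 0 or 1 at 24 h. Subscripts T and C are LAT8881 and placebo.

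- Rate as written: p + (1 − p)q.
- Difference with equal q: (pT − pC)(1 − q).
- Share of placebo responders who are late resolvers: (1 − pC)q / [pC + (1 − pC)q].

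With pT = 0.30 and pC = 0.10, the difference in held responses is 0.20.

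| q (both treatments) | LAT8881 as written | Placebo as written | Difference | Late share, placebo |
|---|---|---|---|---|
| 0.1 | 0.37 | 0.19 | 0.18 | 47% |
| 0.2 | 0.44 | 0.28 | 0.16 | 64% |
| 0.3 | 0.51 | 0.37 | 0.14 | 73% |
| 0.5 | 0.65 | 0.55 | 0.10 | 82% |

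At q = 0.2 the placebo late share is 0.90 × 0.2 / 0.28 = 0.18/0.28 = 64%. The rate ratio falls from 3.0 to 0.44/0.28 = 1.57.

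**Precision.** Take the planned 20 completers as 20 pairs with independent responses (an assumption). SE = √[(b + c − d²)/20], where b and c are the two discordant proportions and d is their difference.

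- Held responses only: b = 0.30 × 0.90 = 0.27, c = 0.10 × 0.70 = 0.07, SE 0.122, d/SE = 0.20/0.122 = 1.63.
- As written, q = 0.2: b = 0.44 × 0.72 = 0.317, c = 0.28 × 0.56 = 0.157, SE 0.150, d/SE = 0.16/0.150 = 1.07.

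**Unequal q.** The difference is (pT − pC) + (1 − pT)qT − (1 − pC)qC. It stops shrinking once qT/qC exceeds (1 − pC)/(1 − pT) = 0.90/0.70 = 1.29. For example, suppose half of late attacks resolve and rescue is used by 45% of LAT8881 and 60% of placebo non-responders. Then qT = 0.5 × 0.55 = 0.275 and qC = 0.5 × 0.40 = 0.20. The written rates are 0.4925 and 0.28, and the difference is 0.2125, above 0.20. The SE is 0.150, so d/SE is 1.41.

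**The case against.** **A reader might infer that the treatment difference is diluted.** The documents do not support that as a general statement. Rescue is open from 2 h and disqualifies, and rescue need against placebo is itself an exploratory objective. If LAT8881 reduces rescue, or acts late, the written difference can hold or grow, as shown above. This objection stands. It does not repair the label: part of such a gain is lower rescue use, which Protocol 10.4 lists separately, and in the example d/SE is still below that for held responses (1.41 against 1.63).

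**A reader might also infer that natural endings make up most sustained responders.** No rates are given. Under the assumed rates, late resolvers are the majority on placebo once q exceeds 0.10/0.90 = 0.11, but on LAT8881 only once q exceeds 0.30/0.70 = 0.43. Nor does Protocol 3.1 say that untreated attacks usually end within 24 h. It gives a 4 to 72 h range for migraine without aura, with no distribution.

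**A 2 h start would be the reviewer's preference.** This stands. The protocol's own pain-free objective runs to 8 h, and a 2 h rule would discard subjects who become free at 4 h or 8 h and stay so. If 10% were free at 2 h on both treatments and late rescue-free resolution were 40% against 20%, a 2 h rule would show no difference, while the written rule would show 0.90 × 0.20 = 18 points. This is the first migraine study of the drug, and the documents give no time course of relief in patients.

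**Late resolvers are already visible.** The first pain-free table, the Kaplan-Meier curves and the listings will show them. That is true, but they also stay inside the sustained percentage.

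**The endpoint is exploratory, with no test and no sample-size basis.** This stands and limits the weight of the point.

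**Conclusion.** The definition does not measure sustained pain freedom. As written it is pain-free at 24 h without rescue, and a subject in pain at every score through 8 h can meet it on one reading. This follows from the text and needs no assumed rate.

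The effect on the comparison is conditional. If late rescue-free resolution is equally likely on both treatments, the difference shrinks by the factor (1 − q): by 10% to 50% for q of 0.1 to 0.5, and from 20 to 16 points in the 30% against 10% example with q = 0.2. If rescue use or late effect differs by treatment, the direction is open. The primary analysis and the sample size are untouched.

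**What to change.** In SAP 7.4 and 10.15.2, and in Protocol 10.4 and the synopsis at the next amendment, define sustained pain-free by three conditions:

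- NRS 0 or 1 first reached at or before 8 h, the window of the protocol's own pain-free objective;
- NRS 0 or 1 at every later recorded score, including 24 h;
- no rescue medication.

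Keep the present quantity as a separate row labelled pain-free at 24 h without rescue. Optionally add a row for subjects already pain-free at 2 h, the last scheduled score before rescue can take effect.

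In the same revision, restore the 24 h pain-free condition in SAP 10.15.2 and correct the cross-reference in 11.8.3.1 to that section. Until the protocol is amended, record the change in SAP 8.1. Make it before database lock, when treatment allocation is disclosed.

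The cost is wording and one or two table rows from scores already collected. The protocol edit goes through the amendment procedure in Protocol 15.1.4. The reported sustained rate will be lower, or at best unchanged.

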Further details of the statistical methodology to be used in the analysis and reporting of the study results, including methods for handling missing data, and early withdrawals, will be provided in a statistical analysis plan that will be finalised prior to database lock.

Anticipated study Duration: Approximately 9 months

Participant duration: Maximum participation duration is 14 weeks (98 days): Screening (28 - 35 days), Treatment period 1 (28 days), Treatment period 2 (28 days), followup (7 days)

2. Study schedule of assessments and procedures

	Screening	Treatment period 1			End of period 1	Treatment period 2			End of period 2, early withdrawal	End of study
Visit no	1	2			3			4	5 (phone)	
Study day	-28 to -1 (+7days)	1	Telephone (if required)	Headache episode	29 ± 2 ¹	Telephone (if required)	Headache episode	57 ± 2 ¹	64 ± 2 ²	
Written informed consent	X									
Eligibility assessment	X									
Confirmation of eligibility		X								
Enrolment and randomisation		X								
Medical history, demographics	X									
Height and weight	X									
12 lead ECG	X	X			X			X		
Pregnancy test ³	X	X				X				
Vital signs	X	X			X			X		
Physical examination	X ⁴	X ⁵			X ⁵			X ⁵		
Clinical laboratory safety testing ⁶	X	X			X			X		
Concomitant medications	X	X	X	X	X	X	X	X	X	
IMP issued		X				X				
IMP administration ⁷				X			X			
Adverse event assessment			X		X	X		X	X	
Headache diary ⁸	X			X			X	X		
Migraine diary ⁹	X			X			X			
Patient satisfaction survey					X			X		

1 Or maximum 5 business days after dose of IMP

2 Or 7 days after Visit 4

3 Females of child bearing potential only, blood test at screening, urine other occasions

4 Full physical examination

5 Targeted physical examination

6 Haematology, biochemistry, urinalysis

7 Migraine episode only

8 Headache diary during both non-migraine and migraine headaches

9 Migraine diary, during migraine headaches

3. Introduction and background information

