14.5.1 Analgesic use

Rescue medication use over the treatment period will be listed for each subject.

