#### 11.8.2.6 Migraine and Headache Diary

Migraine and headache diary details will be listed by subject. Menstrual cycle details will also be listed by subject.

In DDP: Listing 16.2.6.1, Listing 16.2.6.2 and Listing 16.2.6.5

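### The 24-hour sustained pain-free endpoint requires no relapse, but nothing is scored between 8 and 24 hours and the SAP names no other source, so an unrescued relapse that settles in that gap can pass as a success

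*Protocol*

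**What the plan says.** Protocol 10.4 defines the exploratory endpoint by three conditions: no migraine pain at 24 hours, plus "no use of rescue medication and no relapse of headache pain within 24 hours (24-hour sustained pain-free) after administration".

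Protocol 11.5.1 has pain recorded in the migraine diary at dosing (t = "0 min) and at 0.5, 1.0, 1.5, 2, 4, 8 and 24 hours post dose". It adds: "Pain should reflect the subject's pain at the time of recording". SAP 10.3 lists the same analysis timepoints.

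Subjects keep a second diary. Protocol 9.3: "The headache diary will be used to record menstrual cycles and onset and nature of headaches (both migraine and non-migraine"). A footnote to the schedule in Protocol section 2 says when it is filled in: "Headache diary during both non-migraine and migraine headaches". It is not tied to hours after dosing.

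On rescue, Protocol 14.5.1 states: "Rescue medication use over the treatment period will be listed for each subject".

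SAP 10.15.2 builds the flag from "Subjects having no use of rescue medication and no relapse of headache pain within 24 hours after administration of IMP". It gives no definition of relapse and no data source. SAP 11.8.2.6 gives the only stated use of the diary details: "Migraine and headache diary details will be listed by subject".

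**The concern.** Two of the three conditions can be read directly from the records: the 24-hour score shows pain at 24 hours, and the medication record shows rescue. The third covers the whole period, and the scheduled scores sample it at a few moments. The last two of those moments are 16 hours apart.

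Take a subject who scores 0 or 1 at 8 hours, has pain from 12 to 18 hours, takes no rescue, and scores 0 or 1 at 24 hours. That subject passes every scheduled check. Only a headache-diary entry would reveal the relapse, and the SAP does not say that such an entry counts.

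Recurrence is what this endpoint adds to the pain-free percentages at each timepoint. SAP 11.8.3.1 reports it with a paired LAT8881 minus placebo difference. If relapses in the gap are missed, the percentage describes subjects who were pain-free when asked and took no rescue, yet it would be read as evidence of a lasting response.

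**Working it through.** **The plan's own figures.** The documents give no expected value or precision for this endpoint, and Protocol 14.2 states that no formal sample size estimation was done. The only planning figures are 20 completers, 20% loss and 26 enrolled (Protocol 5.4). The inflation gives 20/(1 − 0.20) = 25, close to the 26 stated. Nothing below depends on the 26; the 20 is used only as a denominator.

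**Step 1: the unscored time.** Scores fall at 0, 0.5, 1, 1.5, 2, 4, 8 and 24 h. The intervals are 0.5, 0.5, 0.5, 0.5, 2, 4 and 16 h. The longest is 16 h, and 16/24 = 67% of the period.

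**Step 2: which relapses the scores miss.** Assume that a relapse starts at a time S uniform on 8 to 24 h, lasts D hours, is not treated with rescue and is not captured by the headache diary. It is unseen if it ends before the 24 h score, that is, if S < 24 − D. Hence

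unseen share = (24 − D − 8)/16 = (16 − D)/16 for D up to 16, and 0 beyond.

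| D (hours) | Unseen share |
|---|---|
| 4 | 12/16 = 75% |
| 8 | 8/16 = 50% |
| 12 | 4/16 = 25% |
| 16 or more | 0% |

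The documents give no duration for recurrences. Protocol 3.1 describes migraine without aura as lasting 4–72 h, so both the partly visible and the fully visible ranges are plausible.

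**Step 3: effect on a reported percentage.** Let q be the share of subjects who are pain-free at 8 and 24 h but have an unrescued relapse that settles in between. Let s be the share of those relapses that are entered in the headache diary and used for the flag. The overstatement is 100 × q × (1 − s) points. All values of q and s are assumed.

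| q | s = 0 | s = 0.5 | s = 1 |
|---|---|---|---|
| 2% | 2 | 1 | 0 |
| 5% | 5 | 2.5 | 0 |
| 10% | 10 | 5 | 0 |

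With 20 completers, one misclassified subject moves a treatment's percentage by 1/20 = 5 points.

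**Step 4: what the texts say about sources.**
- The migraine diary, as described in Protocol 9.3 and 11.5.2, holds pain and symptom scores, concomitant medications and vomiting. No question about return of pain is described.
- The headache diary could show a return, because it is filled in during any headache. However, no instruction says that a return of the already treated attack is entered as a new onset.
- SAP 10.15.2 and 11.8.3.1 do not refer to the headache diary.
- The SAP sends several open questions to the blinded review: missing baselines (10.12.2), off-schedule times (10.15.3) and menstrual category (10.18). It does not send relapse there.

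**The case against.** The strongest reply is that there are two diaries. The headache diary follows events rather than the clock, so a return at 14 hours should appear in it. Diaries are reviewed at Visit 3 and brought back at Visit 4, each due within 5 business days of dosing. A relapse treated with rescue already fails the endpoint. SAP 10.15.2 does not restrict relapse to NRS scores, whereas 10.15.4 and 10.15.5 do tie their flags to an NRS of 0 or 1. Listing a diary does not bar its use in a derivation. The diary forms are not in the documents, so a recurrence item may exist that the text does not describe.

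Most of this stands, and it rules out two stronger readings that a reader might infer. The first is that the endpoint cannot be checked at all, so that every headache returning in the gap counts as a success. The documents do not support that: rescued relapses fail, relapses still present at 24 h are seen, and the headache diary may catch some of the rest. The second is that the SAP excludes the headache diary. It is silent on the point.

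The reply does not supply a rule. Two programmers working from SAP 10.15.2 could produce different flags, one from scores alone and one from scores plus diary onsets. Nor does it show that a subject would record a return of the same attack as a new headache.

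It is also fair to say that this is one exploratory endpoint in a proof-of-concept study without formal hypotheses, and that the relapse rates and durations used above are assumptions.

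**Conclusion.** The point holds in a limited form. The no-relapse condition spans 24 hours, 16 of which have no scheduled score, and the SAP flag names nothing to fill the gap. An unrescued relapse that settles between 8 and 24 hours is counted as a success unless it is both entered in the headache diary and used for the flag. Neither is assured.

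The size of the overstatement is unknown. The unseen share of unrescued relapses ranges from 75% at 4 h to 0% at 16 h or more, assuming uniform onset and no headache-diary capture; any capture that is used lowers it. A reader might go further and infer that the reported percentage is overstated by a known amount, or that a real difference in recurrence between LAT8881 and placebo is hidden. The documents give no recurrence rates on which to base either claim.

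The change is worth making because it is cheap and concerns the one feature that distinguishes this endpoint. No primary or secondary result is affected.

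**What to change.** **In SAP 10.15.2.** Count a relapse if, after the first pain-free score (NRS 0 or 1) and up to 24 h, there is either an NRS above 1 at a scheduled time or a headache-diary onset. Classify non-migraine entries at the blinded review. In the same edit, restate the protocol's condition of no pain at 24 h, which 10.15.2 omits, and correct the cross-reference in SAP 11.8.3.1, which points to 10.15.1 for this definition.

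**If the diary can be amended before the first subject is dosed**, so that both crossover periods use the same form, add to the 24-hour entry: *Since your 8-hour score, did your headache come back? If yes, when and how bad (0–10)?* Count a reported worst score above 1 as a relapse, in line with the pain-free cut-off in SAP 10.15.4.

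**If the diary cannot be changed**, use the headache-diary onsets and label the result 'pain-free at 24 h without rescue and without recorded recurrence'.

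**Cost.** The SAP change is a short edit and needs no new data. The diary question needs a small amendment with ethics review and relies on recall over 16 hours. Reported percentages may be slightly lower.
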